11.1 Adverse Event Definitions

Adverse Event (AE): any new, undesirable medical experience or change of an existing condition that occurs during or after treatment, whether or not considered product-related.

Serious Adverse Event (SAE): An AE occurring at any dose that results in any of the following outcomes (CFR 312.32)

- Death
- Life-threatening adverse experience
- Inpatient hospitalization or prolongation of existing hospitalization excluding those for study therapy administration, transfusional support, disease staging/re-staging procedures, thoracentesis / paracentesis, or placement of an indwelling catheter, unless associated with other serious events
- Persistent or significant disability or incapacity
- Congenital anomaly / birth defect.

The definition of SAE also includes important medical event. Medical and scientific judgment should be exercised in deciding whether expedited reporting is appropriate in other situations, such as important medical events that may not be immediately life-threatening or result in death or hospitalization but may jeopardize the patient or may require intervention to prevent one of the other outcomes listed in the definition above. These should also usually be considered serious. Examples of such events are intensive treatment in an emergency room or at home for allergic bronchospasm; blood dyscrasias or convulsions that do not result in hospitalization; or development of drug dependency or drug abuse. A new diagnosis of cancer during the course of treatment should be considered an important medical event.

Causality: the relationship of each AE to study drug will be defined as “unrelated” or “related” to study treatment using the following definitions:

- **Unrelated:** There is little or no possibility that the study treatment(s) caused the reported AE; and other factor(s) including concurrent illnesses, progression and expression of the disease state, concurrent medications, or a reaction to concurrent medications appear to explain the AE.
- **Related:** There exists at least a reasonable possibility that the study treatment(s) caused or contributed to the AE; an inability to identify an alternate etiology for an AE should not, by itself, justify a “related” attribution.

Unexpected Adverse Event: An AE that is not mentioned in the Investigator's Brochure or package insert or the specificity or severity of which is not consistent with the investigator's brochure or package insert.

Life-threatening: Any adverse experience that places the patient or subject, in the view of the investigator, at immediate risk of death from the reaction as it occurred. It does not include a reaction that, had it occurred in a more severe form, might have caused death.

AEs will use the descriptions and grading scales found in the revised Common Terminology Criteria for Adverse Events (CTCAE) version 5.0

11.2 Adverse Event Reporting

Study site personnel must notify the PI and the sponsor immediately of any SAE experienced by a patient. In general, SAEs assessed as clearly being due to disease progression, and not due to study drug(s), should be excluded from AE reporting. Study-specific clinical outcomes of death because of disease progression are exempt from SAE reporting, unless the investigator deems them related to use of the study drug. Hospitalization for study drug administration is not an SAE.

The following steps will be taken to report promptly and document accurately any SAE, even if it may not appear to be related to the study treatment:

- Report the SAE to the PI and the treating physician by email, telephone or fax within 24 hours of becoming aware that a patient has experienced an SAE.
- Record the SAE accurately on the AE page of the patient's CRF.
- Using the standard IRB-SAE report form, submit all known patient information within 24 hours of SAE occurrence to the clinical trial office to submit to IRB and

DSMC. Date and sign each report before submission. Include the following information (or as much as possible to obtain and still report the event within 24 hours):

- Study protocol number and indication
- Study site and investigator's identification
- Patient's ID (patient number and initials), age or date of birth, and sex
- Date of enrollment
- Description of SAE, including date of onset and duration, severity, and outcome
- Date of first and most recent (last) dose administered
- Action taken regarding study treatment
- Relationship of SAE to study treatment
- Concomitant medications, including regimen and indication
- Intervention, including concomitant medications used to treat SAE
- Pertinent laboratory data/diagnostic tests conducted and date
- Pertinent medical history of patient
- Date of hospital admission/discharge
- Date of death (if applicable)

Within 10 days of initial IRB notification, the PI is required to submit a completed Adverse Event Report to the IRB. The treating physicians should perform appropriate diagnostic tests and therapeutic measures and submit all follow-up substantiating data, such as diagnostic test reports and autopsy report to the PI, IRB, and DSMB.

Reporting to Celldex is required in addition to reporting to the FDA and does not replace the requirement to notify the FDA if required. The PI will inform Celldex in writing using an SAE form or MEDWATCH 3500A form of any SAE within 24 hours of being aware of the event. The written report must be completed and supplied to Celldex by facsimile or email within 24 hours/1 business day. The initial report must be as complete as possible, including an assessment of the causal relationship between the event and the investigational product(s), if available. Information not available at the time of the initial report (e.g., an end date for the adverse event or laboratory values received after the report) must be documented on a follow-up report.

Completed SAE reports are to be submitted to:

Celldex Therapeutics, Inc.

Pharmacovigilance

[contact]

Email: [contact] (note - check for removal of HIPAA identifiers prior to sending information.

For questions regarding SAE reporting: [contact] (SAE Hotline)

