4 patients who received CDX-1140 monotherapy experienced severe treatment-related pneumonitis, with 3 of the 4 developing pneumonitis during the first week of treatment. These patients developed shortness of breath, and imaging of the lungs demonstrated new inflammatory changes. Two patients required intubation. All four patients were treated with high dose corticosteroids, and two of the patients subsequently died, due to a documented infection in one patient and presumed infection in the other. Two patients demonstrated clinical improvement temporally associated with the administration of tocilizumab. Of note, tocilizumab has not been incorporated into the treatment guidelines for management of pneumonitis associated with immune checkpoint blockade therapy,¹⁰² but there is a case series suggesting that tocilizumab is effective in the management of corticosteroid-refractory pneumonitis irAEs¹⁰³. Based on the rapid response temporally associated with the administration of tocilizumab in the cases discussed above, and the case series suggesting that tocilizumab may be beneficial in treating checkpoint-related pneumonitis, tocilizumab should be considered as a therapeutic option in those patients with CDX-1140 related, steroid-refractory pneumonitis, as well as for other high grade steroid-refractory adverse events.

Thrombosis

CD40 is functionally expressed on platelets and endothelial cells, and CD40 signaling could theoretically promote a pro-thrombotic state. In the CDX1140-01 study, 1 patient developed a deep vein thrombosis and pulmonary embolism that was considered related to CDX-1140. Administration of CP-870,893, another agonist anti-CD40 mAb, was associated with transient increases in D-dimer and thrombin-antithrombin 3 complex formation levels at the 2 highest doses tested (0.2 and 0.3 mg/kg) in the Phase 1 study⁶³. Standard coagulation parameters were not affected by CP-870,893. One patient with a prior history of deep vein thrombosis had a drug-related thromboembolic dose-limiting toxicity.

Elevated liver enzymes

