7.2 DLT Definition

The definition of a dose-limiting toxicity (DLT) will be nearly identical to the definition used in the recent study combining CDX-301 and CDX-1140⁷⁰. A DLT will be defined as any of the following outcomes, attributed to study therapy (including SBRT) and occurring within 8 weeks after initiation of initial study therapy:

- Death
- Any \geq Grade 3 non-hematological toxicity, with the following exceptions:
 - Grade 3 alopecia, vitiligo, or endocrinopathies controlled by hormone replacement therapy
 - Grade 3 nausea that resolves to \leq grade 2 with or without treatment within 72 hours
 - Grade 3 vomiting and diarrhea that resolves to \leq grade 2 with or without treatment within 72 hours
 - Grade 3 fatigue that resolves to \leq grade 2 within 5 days
 - Grade 3 hypertension in the absence of maximal medical therapy
 - Grade 3 adverse event of tumor flare (defined as local pain, irritation, or rash localized at sites of known or suspected tumor) of \leq 7 days in duration
 - Grade 3 amylase or lipase abnormalities that are not associated with symptoms or clinical manifestations of pancreatitis. It is recommended to consult with the Principal Investigator for grade 4 amylase or lipase abnormalities
 - Grade 3 clinically significant laboratory abnormalities that are asymptomatic and can be reversed within 72 hours, however:
 - Any Grade 4 ALT or AST elevation will be a DLT
 - Any Grade 3 ALT or AST elevation that lasts longer than 7 days will be a DLT
 - ALT or AST $> 8 \times$ ULN regardless of duration will be considered a DLT
 - ALT or AST $> 5 \times$ ULN that lasts longer than 14 days will be considered a DLT
 - ALT or AST of $> 3 \times$ ULN with a concurrent total bilirubin $> 2 \times$ ULN will be considered a DLT in the absence of another cause (other than study drug) of these elevations.
- Any of the following hematologic toxicities:
 - Grade 4 anemia (regardless of duration)
 - Grade 4 neutropenia persisting > 5 days
 - Grade 3 thrombocytopenia with hemorrhage
 - Grade 4 thrombocytopenia
 - Any other \geq Grade 3 hematologic adverse event not returning to baseline or \leq grade 1 prior to the next planned study drug dose, excluding asymptomatic lymphopenia which will not be considered a DLT
- \geq Grade 3 infusion reaction
 - Excluding grade 3 infusion reactions resolving within 6 hours with or without treatment

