11.0 ADVERSE EVENTS

An adverse event (AE) is any untoward medical occurrence in a subject administered a study treatment. An AE can therefore be any unfavorable and unintended sign (including an abnormal laboratory finding), symptom, or disease temporally associated with the use of a study treatment, whether or not related to the study treatment. All observed or volunteered AEs regardless of suspected causal relationship to the study treatment will be reported as described in the following sections. For the purposes of this current study, "study treatment" is defined as CDX-1140, CDX 301, and radiotherapy. AEs for subjects on arm 2 who receive standard therapy (e.g., chemotherapy) will also be reported.

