13.3 Appendix C – iRECIST Criteria

Tumors may respond differently to immunotherapies compared with chemotherapeutic drugs, raising questions about the assessment of changes in tumor burden—a mainstay of evaluation of cancer therapeutics that provides key information about objective response and disease progression. Immunotherapeutics may result in infiltration of immune cells leading to transient increase in the size in malignant lesions, or undetectable lesions becoming detectable. A consensus guideline—iRECIST—was developed by the RECIST working group for the use of modified Response Evaluation Criteria in Solid Tumors (RECIST version 1.1) in cancer immunotherapy trials, to ensure consistent design and data collection, facilitate the ongoing collection of trial data, and ultimate validation of the guideline⁸⁴. This guideline describes a standard approach to solid tumor measurements and definitions for objective change in tumor size for use in trials in which an immunotherapy is used. The criteria are identical to those of RECIST 1.1 in many respects but have been adapted to account for instances where an increase in tumor burden, or the appearance of new lesions, does not reflect true tumor progression.

To assess objective response or future progression, it is necessary to estimate the overall tumor burden at baseline and use this as a comparator for subsequent measurements. All baseline evaluations should be performed as close as possible to the treatment start and never more than 4 weeks before the beginning of the treatment. Assessments should be identified on a calendar schedule and should not be affected by delays in therapy. The same method of assessment and the same technique should be used to characterize each identified and reported lesion at baseline and during follow-up. Imaging based evaluation should always be done rather than clinical examination, unless the lesion(s) being followed cannot be imaged but are assessable by clinical exam. (See “Methods of Lesion Measurement” for further guidance.)

Measurable Disease:

Measurable tumor lesions (nodal, subcutaneous, lung parenchyma, solid organ metastases) are defined as those that can be accurately measured in at least one dimension (longest diameter to be recorded) as ≥ 20 mm with chest x-ray and as ≥ 10 mm with CT scan or clinical examination.

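### The exclusion of progression-attributed SAEs from AE reporting in section 11.2 contradicts the protocol's own all-SAE text, and a treatment-related event misread as progression could be lost from the safety record

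*Combined protocol and SAP*

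**What the plan says.** Section 11.2 gives the exclusion, which is to apply in general: "SAEs assessed as clearly being due to disease progression, and not due to study drug(s), should be excluded from AE reporting". A separate sentence deals with deaths from progression, which are "exempt from SAE reporting, unless the investigator deems them related to use of the study drug".

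Other text points the other way:

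- Later in section 11.2, steps are set out to "report promptly and document accurately any SAE, even if it may not appear to be related to the study treatment". They include entry on the AE page of the CRF and submission of a report for the IRB and DSMC. The last part of 11.2 requires the manufacturer to be told of any SAE within 24 hours and makes no exception for progression.
- Section 11.0: "All observed or volunteered AEs regardless of suspected causal relationship to the study treatment will be reported". That sentence goes on to refer to the sections that follow it.
- Section 11.1 allows two attributions, related and unrelated. Progression of the disease is one of the listed explanations for an unrelated event.
- Section 7.1 has AEs scored and attributed at each visit in both arms so that rates can be compared between arms.

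Section 8.1 states that neither subjects nor personnel are blinded. Section 10.4 has the DSMC review grade 3 or higher AEs, and all Phase I safety data before Phase II starts. No section describes adjudication of a progression label.

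**The concern.** A site cannot both exclude a progression-attributed SAE from AE reporting and enter any SAE on the AE page. Some sites or staff will follow one sentence and some the other, so the AE data may be incomplete in a way that nobody can see afterwards.

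This matters more here than in most oncology trials because the protocol itself says that apparent progression may not be progression. Appendix C adopts iRECIST to "account for instances where an increase in tumor burden, or the appearance of new lesions, does not reflect true tumor progression". One known serious toxicity can also look like lung cancer getting worse. On the severe CDX-1140 pneumonitis cases, section 5.2.6 says: "These patients developed shortness of breath, and imaging of the lungs demonstrated new inflammatory changes".

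At stake is whether such an event, once labelled as progression, stays in the record where the DSMC can see it and the label can be corrected.

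**Working it through.** The plan gives no figure on this point, so the check is mainly textual.

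**1. Scope of the exclusion.** The two sentences in 11.2 use different terms. Progression deaths are exempt from SAE reporting; other progression SAEs are excluded from AE reporting. As written, the second is the wider exclusion. It has two conditions, both required: the event is clearly due to progression, and it is not due to study drug(s). It opens with a general qualifier and does not name the assessor.

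**2. Is it needed?** Under 11.1, an event explained by progression is a reported AE with an unrelated attribution. The existing scheme therefore already handles these events by recording and attributing them. Removing them adds nothing that the attribution does not provide.

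**3. Timing of the judgement.**
- SAE report: within 24 hours (11.2).
- DLT window: 8 weeks from the start of therapy (7.2).
- First scheduled CT: week 9, plus or minus 1 week (4.2.2), so weeks 8 to 10. At the earliest this is the last week of the DLT window.
- Confirmation of iUPD: 4 to 8 weeks later (Appendix C). From week 9 this is week 9 + 4 = 13 to week 9 + 8 = 17.
- Three of the four severe pneumonitis cases arose in the first week of treatment (5.2.6). The first CDX-1140 dose here is in week 2, so a similar case would fall in about week 2 or 3, at least 9 − 3 = 6 weeks before the nominal first scan.

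Section 7.3 allows extra imaging at any time, but the scheduled scans will rarely inform the label. Nothing in the documents tells a site to restore an SAE already excluded as progression when later imaging does not support it.

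**4. SBRT.** The exclusion tests only study drug(s). Section 11.0 defines study treatment to include radiotherapy, and 7.2 counts toxicity from SBRT. The second condition therefore leaves out one of the three components of study therapy.

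**5. Can the effect be sized?**
- Pneumonitis rate: 4 cases over the 55 monotherapy patients in section 2.5 is 4/55 = 7.3%, or 23 × 4/55 = 1.7 cases in 23 Arm 1 subjects. Over all 89 treated patients it is 4/89 = 4.5%, or 23 × 4/89 = 1.0. Both assume that the cases belong to the May 2020 data cut. All four were on monotherapy; section 5.2.6 lists none among patients given the combination with CDX-301 (31 patients, section 2.5), which is the drug pairing in Arm 1.
- Acceptance under the rule in 8.2 (4 or fewer DLTs in 23): P = Σ C(23,x) qˣ(1 − q)²³⁻ˣ for x = 0 to 4. At q = 0.35 this is 5.5%, against the plan's stated maximum of 5%.
- If an assumed share m of true DLTs went uncounted, q = 0.35(1 − m). For m = 10%, 20% and 30%, q = 0.315, 0.28 and 0.245, and P = 10.5%, 18.6% and 30.2%.
- The documents give no value for m. Moreover, 7.2 counts only events attributed to study therapy, so an event misread as progression leaves the DLT count whether or not 11.2 removes its record. These acceptance figures are therefore not an effect of 11.2.

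**The case against.** The best defence is that the exclusion is narrow and the rest of the protocol contains it. Both conditions must hold, and 11.1 calls an event related when there is at least a reasonable possibility of causation. Dyspnea with new lung changes soon after CDX-1140 should not pass as clearly due to progression. Section 5.2.6 warns of pneumonitis and asks for neoplastic and infectious causes to be ruled out when an immune-related event is suspected. The all-AE sentence in 11.0 defers to the sections after it, so it need not conflict with 11.2. The any-SAE steps may keep these events on the CRF in practice.

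Most of this stands as a limit on the point. An event recognised as ambiguous remains reportable, and it is not established that progression-attributed SAEs vanish entirely. It does not remove the conflict: 11.0 defers to 11.2, and 11.2 itself points both ways. Nor does it help with an event that is confidently but wrongly labelled.

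A reader might also infer that such an episode is counted nowhere, because iUPD that later regresses is disregarded for PFS. That is not the usual outcome: under Appendix C, iUPD in a patient who is not clinically stable supplies the PFS date, and an SAE blamed on progression would normally come with clinical instability. Tumor flare is a weak example too. Section 7.2 names it as an adverse event and defines it by local symptoms: "Grade 3 adverse event of tumor flare (defined as local pain, irritation, or rash localized at sites of known or suspected tumor".

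**Conclusion.** The point holds as an internal contradiction in the reporting rules with a plausible route to lost safety data. It rests on the wording alone and needs no assumed misclassification rate. What 11.2 adds to the ordinary risk of misattribution is loss of the record: a progression-labelled SAE may not reach the DSMC, may be missing from the between-arm comparison in 7.1, and cannot readily be re-attributed.

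Two stronger conclusions are tempting and are not supported. The first is that the 4-of-23 safety verdict is compromised. The counts are tight, and one missed DLT turns 5 of 23 into 4 or, in Phase I, 2 of 6 into 1. But that loss comes through the attribution requirement in 7.2. The assumed losses also fit poorly with the pneumonitis data: at 35%, 23 × 0.35 = 8.05 DLTs are expected, and losing 20% or 30% means 1.6 or 2.4 events, against 1.0 to 1.7 projected pneumonitis cases in all. The second is that the exclusion favours Arm 1. It applies to both arms, and section 8.3 assumes faster progression in Arm 2 (median PFS 5 against 10 months), so more SAEs could be excluded there. Neither size nor direction can be derived from the documents.

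**What to change.** Reconcile sections 11.0, 11.1 and 11.2:

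- Limit the progression exemption to expedited reporting.
- State that every SAE in both arms is recorded on the AE page of the CRF with its attribution, including those attributed to progression.
- List progression-attributed SAEs for the DSMC, and allow re-attribution when later imaging does not support progression, keeping both the initial and the revised attribution.
- Replace study drug(s) with study treatment in the exemption, so that SBRT is covered.

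Do not reclassify SAEs automatically by PFS status. A patient who deteriorates from true progression without a qualifying scan, a situation that Appendix D recognises, would then be counted as having had an adverse event of the treatment period.

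The cost is protocol wording, a few more CRF entries and a longer SAE listing. No new assessments are needed, and patient care does not change.

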13.0 APPENDICES

13.1 Appendix A - ECOG Performance Status

Grade	ECOG
0	Fully active, able to carry on all pre-disease performance without restriction.
1	Restricted in physically strenuous activity but ambulatory and able to carry out work of a light or sedentary nature, e.g., light house work, office work
2	Ambulatory and capable of all selfcare but unable to carry out any work activities. Up and about more than 50% of waking hours.
3	Capable of only limited selfcare, confined to bed or chair more than 50% of waking hours.
4	Completely disabled. Cannot carry on any selfcare. Totally confined to bed or chair.
5	Dead

Adapted from Oken 1982¹¹⁶.

13.2 Appendix B – Common Terminology Criteria for Adverse Events Version 5.0

https://ctep.cancer.gov/protocoldevelopment/electronic_applications/docs/CTCAE_v5_Quick_Reference_5x7.pdf

